9.6 Reporting of Adverse Events to Genentech

For all Safety Reporting information please refer to the authorised Safety Data Exchange Agreement (referred to as "SDEA") which describes the procedures and time frames and defines the responsibilities between the University of Leicester and Genentech to ensure compliance with the applicable laws and regulations pertaining to safety reporting and its related activities, as well as related activities for the trial. The Funder (Genentech) who is remaining blinded, and an Independent Data Monitoring Committee (IDMC), who is unblinded, share the responsibility for regularly monitoring the overall safety of patients in the trial.

Adverse events related to the Genentech drug MSTT1041A (Anti-ST2) might potentially disclose important safety information. The investigator should copy Genentech into all communications when expediting SARs or SUSARs to the Sponsor, health and regulatory authorities in accordance with Sponsor Safety Reporting SOPs and should report all SARs related to Genentech's product to the local affiliate safety department within the time-frame as agreed upon in the SDEA.

- Serious AE reports that are related to the product or where the causality is assessed as unknown or not provided shall be transmitted to Genentech within fifteen (15) calendar days of the awareness date, except for life-threatening or fatal SADRs which shall be transmitted to Genentech within seven (7) calendar days of the awareness date.
- All deaths in which causality is unrelated to product shall be transmitted to Genentech within (15) calendar days of the awareness date.
- Serious AE reports that are unrelated to the product shall be transmitted to Genentech within thirty (30) calendar days of the awareness date. This would include pregnancy reports where the foetus may have been exposed to the trial drug, and follow up until the outcome of the pregnancy is known, whenever possible based upon due diligence taken to obtain the follow-up information.

Page 31 of 60

- Adverse Events of Special Interest (AESI) (serious or non-serious) are a subset of Events to Monitor (EtMs) of scientific and medical concern specific to the Funder's product or program, for which ongoing monitoring and expedited reporting to Genentech are required. Separate reporting forms have been provided by Genentech to capture these which will also be captured on the trial database. AESIs for this trial, which will include Major Adverse Cardiac Events (MACE) and Anaphylaxis (related or possibly related to Genentech product), shall be forwarded to Genentech within fifteen (15) calendar days of the awareness date. Others (non-related to Genentech product) shall be sent within thirty (30) calendar days. For further information please refer to the SDEA agreement.
- In addition, the following Special Situations Reports should be collected (using the Sponsor SAE reporting from) even in the absence of an AE:
 - Data related to the product usage during pregnancy or breastfeeding, data related to overdose, abuse, misuse or medication error
 - Data related to a suspected transmission of an infectious agent via a medicinal product (STIAMP).

Safety Reporting to Genentech will be done according to the current SDEA.

9.7 Pregnancy and pregnancy reporting

The effects of Anti-ST2 on embryo-foetal development have not yet been studied. Based on current scientific knowledge, embryo-foetal exposure to mAbs (Anti-ST2 type) during organogenesis is understood to be low in humans. It is not known whether Anti-ST2 can cross the placenta or cause harm to the foetus when administered to pregnant women or whether it affects reproductive capacity. As such participants will not be eligible to continue in this trial if they are pregnant, breastfeeding or intent to become pregnant. Two separate contraceptive methods must be declared.

- A woman is considered of childbearing potential (WOCBP), i.e. fertile, following menarche and until becoming post-menopausal unless permanently sterile. Permanent sterilisation methods include hysterectomy, bilateral salpingectomy and bilateral oophorectomy.
- A postmenopausal state is defined as no menses for 12 months without an alternative medical cause. A high follicle stimulating hormone (FSH) level in the postmenopausal range may be used to confirm a post-menopausal state in women not using hormonal contraception or hormonal replacement therapy. However in the absence of 12 months of amenorrhea, a single FSH measurement is insufficient.
- A man is considered fertile after puberty unless permanently sterile by bilateral orchidectomy.

Women of child-bearing potential must have a negative blood serum pregnancy test performed at the screening visit and must agree to use two methods of birth control, (one of which must be a barrier method. However given this disease population and the average

age range, this will not be a significant proportion. Additional testing will also occur at any time during the trial if a menstrual period is missed or as required by local law.

Participants of child bearing potential both male and female will be given clear instructions regarding contraception throughout the trial which will be captured in the CRF. Adequate contraceptive measures have been defined as sterilisation, intra-uterine device, oral contraceptives, consistent use of barrier methods, male sterilisation or true abstinence (when this is in line with the preferred and usual lifestyle of the subject. [Periodic abstinence (such as calendar, ovulation, symptothermal, post-ovulation methods) and withdrawal are not acceptable methods of contraception].

All pregnancies within the trial (either the trial participant or the participant's partner, with participants consent) should be reported to the Chief Investigator, the LCTU and the Sponsor using the relevant Pregnancy Reporting Form within 24 hours of notification

Pregnancy is not considered an AE unless a negative or consequential outcome is recorded for the mother or child/foetus. If the outcome meets the serious criteria, this would be considered an SAE.

The pregnancy must be followed up to determine outcome (including premature termination) and status of mother and child in accordance with Sponsor and local reporting requirements and timelines.

Any SAE occurring in association with a pregnancy, brought to the investigator's attention after the participant has completed the trial and considered by the investigator as possibly related to the trial treatment, must be promptly reported to sponsor in accordance with Sponsor and local reporting requirements and timelines.

Genentech reporting requirements are such that whilst pregnancy reports are not serious AEs or Adverse Drug Reactions (ADRs) per se, any reports of pregnancy (including pregnancy occurring in the partner of a male trial subject), where the foetus may have been exposed to the Product, shall be transmitted to Genentech within thirty (30) calendar days of the awareness date. Pregnancies will be followed-up until the outcome of the pregnancy is known, whenever possible, based upon due diligence taken to obtain the follow-up information.

9.7 Overdose

The dose of anti-ST2 considered to be an overdose has not been defined. There are no known antidotes. The investigator should use clinical judgement in treating the symptoms of a suspected overdose.

9.8 Urgent safety measures

The Sponsor and Investigator may take appropriate urgent safety measures to protect clinical trial participants from any immediate hazard to their health and safety. The measures must be taken immediately; Sponsor, MHRA, REC, HRA and R&D approval is not required before implementation.

Reporting of Urgent Safety Measures should adhere to Sponsor SOPs. Sponsor and the regulatory authorities, Genentech and the LCTU must be informed in writing of the measures taken and the circumstances giving rise to those measures, in the form of a substantial amendment within three days. The process for submitting amendments as a result of Urgent Safety Measures is covered in the Sponsor SOPs.

9.9 The type and duration of the follow-up of participants after adverse reactions.

Following an adverse drug reaction (ADR) the participants will be followed-up for an appropriate length of time as dictated by the nature of ADR and their clinical needs. ADR will continue to be recorded and reported for up to 3 months after the last dose of IMP has been administered. Any SUSAR will need to be reported to the Sponsor irrespective of how long after IMP administration the reaction has occurred until resolved.

9.10 Development safety update reports

Within 90 days following the anniversary of the authorisation date for the trial, a Development Safety Update Reports (DSURs) will be sent by the Chief Investigator to the MHRA and the Main Research Ethics Committee. A copy of the report will also be sent to Genentech (as the trial funder/drug supplier), the University of Leicester (as the trial Sponsor), and all host organisations. The LCTU will prepare the DSUR report on behalf of the CI and submit to the Sponsor who is responsible for reporting to the Competent Authority (MHRA) within the specified time frame.

The LCTU on behalf of the Trial Sponsor (University of Leicester) will also forward quarterly listings of non-serious AEs originating from the Trial to Genentech.

10 STATISTICS AND DATA ANALYSIS

See full statistical analysis plan for further details.

10.1 Sample size calculation

Recruitment of 80 participants with a drop-out rate of 10% will be sufficient to give 80% power at the 5% level assuming either an annualised exacerbation frequency 2 or 2.5 per year in the placebo group to observe a 50% or 40% reduction in exacerbation frequency in those receiving anti-ST2 respectively.

This sample size estimate is based upon a negative binomial model. The estimation of the overdispersion was derived from the BEAT-COPD (Biomarkers to Target Antibiotic and Systemic Corticosteroid Therapy in COPD Exacerbations) [ISRCTN92422949] data and was 1.3 with a mean exacerbation frequency of 2.85.

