#### 1.2.4 Sample size

Recruitment of 80 participants with a drop-out rate of 10% will be sufficient to give 80% power at the 5% level assuming either a 48 week exacerbation frequency 2 or 2.5 per year in the placebo group to observe a 50% or 40% reduction in exacerbation frequency in those receiving anti-ST2 respectively.

This sample size estimate is based upon a negative binomial model. The estimation of the over-dispersion was derived from the BEAT-COPD (Biomarkers to Target Antibiotic and Systemic Corticosteroid Therapy in COPD Exacerbations) [ISRCTN92422949] data and was 1.3 with a mean exacerbation frequency of 2.85.

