# 5.4 Primary Outcome Analysis

#### 5.4.1 Primary Analysis of Primary Outcome

The main approach to primary analyses will be an intention-to-treat (ITT), where the ITT population consist of all randomised participants into the trial (regardless of whether they received trial drug). Descriptive statistics of the estimated exacerbations rates in the 48 week treatment period will be presented by treatment arm and overall (Table 5 in Appendix-1). Histogram of the number of exacerbations in the 48 week period by patient will be drawn to check the distribution of the number of exacerbations during treatment (Figure 5). Cumulative number of exacerbations will be plotted by treatment arm (Figure 6).

A generalised linear model (assuming a negative binomial distribution, which accounts for variability among patients in the number of and frequency of exacerbation) will be fitted for the primary outcome of COPD exacerbations during the 48 week treatment period as an outcome with explanatory variables of treatment arm and number of exacerbation in the 12 months prior to the trial (stratification factor), and log-time on study as an offset. The offset (log-time), allows for different lengths of time on treatment for each participant [2]. This assumes that missing data is missing at random (MAR), and will be applied where all of the available observed data are analysed without deletion nor imputation.

The primary outcome data is assumed to follow a negative binomial distribution with the over dispersion estimated to be 1.3. The primary analysis of the primary outcome will give an estimate of the significance of the dispersion parameter. If the dispersion is found to be non-significant (i.e no evidence of over-dispersion) we will consider the simpler Poisson model where the dispersion parameter equals to zero. The ratio of the exacerbation rates (RR) on the anti-ST2 relative to the placebo, associated two-sided 95% confidence interval (CI) and p-value will be reported (Table 5 in Appendix-1). A value of 1.0 would indicate the same rate as placebo; the lower the ratio the greater reduction in exacerbations compared with placebo. A two-sided p-value  $\leq 0.05$  will be considered as a significant difference in the number of COPD exacerbations in 48 weeks between the two treatment arms.

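### The stated 80% power does not follow if the over-dispersion of 1.3 is the negative binomial parameter SAP 5.4.1 describes: power is then about 53-59% and 35-39%

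*Protocol*

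**What the plan says.** Protocol 10.1 and SAP 1.2.4 give the same calculation, based on a negative binomial model: "Recruitment of 80 participants with a drop-out rate of 10% will be sufficient to give 80% power at the 5% level". The effects are a 50% reduction from a placebo rate of 2 (scenario 1) and a 40% reduction from 2.5 (scenario 2). The over-dispersion comes from an earlier COPD trial and "was 1.3 with a mean exacerbation frequency of 2.85". Neither section defines that quantity or gives the formula, sidedness or exposure time.

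The rate unit differs between the documents. The protocol has "assuming either an annualised exacerbation frequency 2 or 2.5 per year in the placebo group"; the SAP has "assuming either a 48 week exacerbation frequency 2 or 2.5 per year in the placebo group".

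SAP 5.4.1 is the only place that indicates the scale of 1.3: "The primary outcome data is assumed to follow a negative binomial distribution with the over dispersion estimated to be 1.3". The same paragraph continues: "If the dispersion is found to be non-significant (i.e no evidence of over-dispersion) we will consider the simpler Poisson model", with the Poisson case identified as the one "we will consider the simpler Poisson model where the dispersion parameter equals to zero". It also fixes the test as two-sided: "associated two-sided 95% confidence interval (CI) and p-value will be reported".

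**The concern.** A parameter that is zero for Poisson data is k in variance = mu + k*mu^2. A variance/mean ratio would be 1 for Poisson data. SAP 5.4.1 uses over-dispersion and dispersion for what reads as one parameter and gives its value as 1.3, so the natural reading is k = 1.3. That is heavy over-dispersion for means of 1 to 2.5, and about 36 patients per arm then looks too few for 80% power.

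The 80% figure is the trial's stated sensitivity for its single primary analysis. If it is wrong, a non-significant result could be taken as good evidence against a 40-50% reduction when it is not.

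**Working it through.** **Inputs.** 40 per arm (80 randomised 1:1, Protocol 7.5), or 36 after 10% drop-out. Rates 2 to 1 (RR 0.5) and 2.5 to 1.5 (RR 0.6). Two-sided 5%, z = 1.96. Exposure t = 1 year, or 48/52 if the rates are annual and the count covers 48 weeks (SAP 2.1.1).

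**Formula.** For the log rate ratio, with n per arm:

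- k reading: V1 = [1/(mu0*t) + 1/(mu1*t) + 2k]/n
- variance/mean reading (ratio 1.3 at every mean): V1 = 1.3*[1/(mu0*t) + 1/(mu1*t)]/n
- power = Phi((|log RR| - 1.96*sqrt(V0))/sqrt(V1))

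The documents do not give the null variance V0, so three choices were used: V0 = V1 (Wald), both arms at the mean of the two rates (pooled), and both arms at the placebo rate (placebo).

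**Worked cases, n = 36, t = 1, Wald.**

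- k = 1.3, scenario 1: V1 = (0.5 + 1 + 2.6)/36 = 0.1139, SE 0.3375; (0.6931 - 0.6615)/0.3375 = 0.094; power 53.7%.
- k = 1.3, scenario 2: V1 = (0.4 + 0.667 + 2.6)/36 = 0.1019, SE 0.3191; (0.5108 - 0.6254)/0.3191 = -0.359; power 36.0%.
- Ratio 1.3, scenario 1: V1 = 1.3*1.5/36 = 0.0542, SE 0.2327; power 84.6%.
- Ratio 1.3, scenario 2: V1 = 1.3*1.0667/36 = 0.0385, SE 0.1963; power 74.0%.

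**All variants at 36 per arm** (scenario 1 / scenario 2, %):

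| Reading of 1.3 | Exposure | Wald | Pooled | Placebo |
|---|---|---|---|---|
| k = 1.3 | 1 year | 53.7 / 36.0 | 55.3 / 36.6 | 58.6 / 38.7 |
| k = 1.3 | 48 weeks | 52.5 / 35.3 | 54.2 / 36.0 | 57.7 / 38.2 |
| variance/mean = 1.3 | 1 year | 84.6 / 74.0 | 87.1 / 76.0 | 91.6 / 81.7 |
| variance/mean = 1.3 | 48 weeks | 81.6 / 70.6 | 84.5 / 72.7 | 89.6 / 78.9 |
| ratio converted at mean 2.85: k = 0.3/2.85 = 0.105 | 1 year | 88.9 / 77.4 | 90.6 / 78.9 | 93.7 / 83.4 |
| ratio converted at mean 2.85: k = 0.105 | 48 weeks | 86.6 / 74.6 | 88.7 / 76.3 | 92.3 / 81.1 |

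If 1.3 were 1/k (k = 0.77), power is 65-72% and 46-52%. No reading tried gives about 80% in both scenarios.

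**Most favourable cases with k = 1.3.** At 40 per arm with no loss: 56.9-62.9% and 38.5-42.1%. The same one-sided, one year: at most 73.4% and 54.1%. In simulations of a negative binomial model with a log-time offset, 40 per arm and 4 per arm leaving at random times, power was 56-57% and 37-41% (Monte Carlo SE about 1.3 points). The reduction detectable with 80% power at 36 per arm is 59-63%.

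**Rate unit.** Going from one year to 48 weeks costs 0.9-1.2 and 0.5-0.7 points on the k reading, and 2.0-3.0 and 2.8-3.4 points on the constant-ratio reading.

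**Precision.** For an observed RR of 0.60 at 36 per arm over one year, the 95% CI is 0.60*exp(+/-1.96*0.3191) = 0.32 to 1.12 with k = 1.3, and 0.60*exp(+/-1.96*0.1963) = 0.41 to 0.88 with a ratio of 1.3.

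**The case against.** **The k reading is an inference.** SAP 5.4.1 gives 1.3 as the over-dispersion and then speaks of the dispersion parameter to be estimated; it does not expressly equate the two. This stands as a caution, and it is why the planners' reading is left open. But treating them as different quantities within one paragraph is strained, and a ratio reading would make that paragraph misleading.

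**A ratio can be reconciled with 80%.** A ratio of 1.3 at the stated mean of 2.85 converts to k = 0.105, which respects the negative binomial form and gives 2.85 a purpose. With the placebo-rate null variance, both scenarios then pass, even over 48 weeks (92.3% and 81.1%). That is correct and is the best case for the plan. It needs a conversion and a formula that neither document states, and over 48 weeks scenario 2 falls to 74.6% and 76.3% under the other two null variances.

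**Covariate adjustment and partial follow-up add power.** The model adjusts for prior exacerbations, but no gain is quantified. For 80% at 36 per arm over one year, residual k would have to fall from 1.3 to 0.35-0.53 (scenario 1) and 0.07-0.16 (scenario 2); an assumed residual k of 1.0 gives 60-66% and 42-45%. Partial follow-up is kept through the offset, and simulating that moves the figures by only a point or two.

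**It is too late to matter.** Recruitment is complete and the current SAP post-dates database lock. No estimate or test changes, and the confidence interval will show the achieved precision. True, but the 80% claim remains in both documents and will frame how a non-significant result is read.

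**Conclusion.** The concern holds. On SAP 5.4.1's own description (k = 1.3, two-sided 5%, no credit for covariate adjustment), power at 36 per arm is about 53-59% and 35-39%. That is more than 20 points short in scenario 1 and more than 40 in scenario 2, and no variant tried closes the gap. The trial would then have little better than an even chance of detecting a 50% reduction and would miss a 40% reduction about six times in ten.

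On a constant variance/mean reading, scenario 1 is met (82-92%). Scenario 2 is 71-82% and, at 36 per arm, reaches 80% only with a full year of exposure and the placebo-rate null variance; converting the ratio to k = 0.105 widens that margin slightly. SAP 5.4.1 would then describe the parameter wrongly. The difference in rate unit is minor on the k reading but can take scenario 2 across 80% on the constant-ratio reading. Either way a correction is needed; the documents do not settle which one.

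**What to change.** Leave the sample size of 80 and the analysis as they are.

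1. Establish from the source-trial data what 1.3 is. The SD at mean 2.85 separates the readings: sqrt(2.85 + 1.3*2.85^2) = 3.66 if k, sqrt(2.85 + 2.85^2/1.3) = 3.02 if 1/k, and sqrt(1.3*2.85) = 1.92 if a variance/mean ratio.
2. Add a dated clarification to Protocol 10.1 and SAP 1.2.4, with the existing text left visible, and repeat it in the report. It should define 1.3 and state the formula, sidedness, exposure and a single rate unit.
3. If 1.3 is k, replace the 80% with the recomputed range (about 53-59% and 35-39% at 36 per arm), or state that 80% power needs roughly a 59-63% reduction. Note that no gain from covariate adjustment is assumed, and that a non-significant result does not by itself rule out a 40-50% reduction.
4. If 1.3 is a variance/mean ratio, correct SAP 5.4.1 and restate the power for each scenario under the stated formula and 48-week exposure.

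The cost is one data check and some wording, with no extra patients. The drawback is that the stated power may become less favourable.

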10.2 Planned recruitment rate

Based on our experience of recruitment, we anticipate a recruitment rate of approximately 3 participants per week. We expect a screen failure rate of 30%.

10.3 Statistical analysis plan

A separate Statistical Analysis Plan (SAP) will contain full details of all statistical analyses and will be prepared early in the trial and finalised prior to database lock.

Reporting of results will be based on the CONSORT statement. A Trial Steering Committee and Data Monitoring Committee will be established, with appropriate charters which will specify their remit.

A total of 80 participants will be randomised in a 1:1 ratio to receive anti-ST2 or placebo. For safety and tolerability, AEs, SAEs, vital signs, physical examinations, ECGs, and clinical laboratory assessments at specific time points will be evaluated. All safety data will be summarised descriptively. Number and percentage of AEs will be presented for each treatment by Preferred Term and System Organ Class of the current Medical Dictionary for Regulatory Authorities (MedDRA) dictionary. Individual listings of all SAEs and AEs leading to investigational product (IP) discontinuation will be summarised using the current MedDRA dictionary. Similar analyses will be performed for potentially significant and clinically important AEs. Number of COPD exacerbations will be summarised using frequency count and percentage.

Summaries and listings of vital signs, physical examination, ECG, and laboratory test results will be presented.

10.4 Summary of baseline data and flow of participants

A diagram of participants flow through the trial has been produced (Appendix 3).

Baseline demographics and measurements will be summarised using number and percentage for categorical data; while continuous variables will be summarised using mean and standard deviation where data follows normality assumptions or median and interquartile range where normality assumptions are not meet. No statistical tests are planned to assess the difference in baseline variables between arms.

The baseline variables that will be summarised include the following:

- Age
- Gender
- Ethnicity
- Frequency of moderate-to-severe exacerbations in the last 12 months
- GOLD COPD stage
- Smoking pack years
- Diagnosed with diabetes mellitus
- History of hypertension
- Previous heart failure (HF)

Page **35** of **60**

